6 ANALYSIS POPULATIONS

The Intent-to-Treat (ITT) population is defined as all subjects randomized into the study who received at least 1 dose of study drug. All ITT subjects will be counted in the group to which they were randomized, regardless of the study drug they were given. All efficacy analyses will be performed on this ITT population, unless otherwise specified.

The Safety population is defined as all subjects enrolled into the study who received at least 1 dose of study drug. All Safety population subjects will be counted in the group corresponding to the study drug received, regardless of randomized assignment. All safety analyses will be performed on this Safety population, unless otherwise specified.

The Per-protocol population will include all subjects in the ITT population, excluding subjects with major protocol deviations that may have an impact on the primary efficacy analyses. The major protocol deviations and the subject's exclusion from the Per-protocol population will be reviewed at a blinded data review meeting and documented prior to the database lock and the study unblinding.

The PK population will include all subjects in the ITT population with evaluable PK data. All PK analyses will be performed on this PK population, unless otherwise specified.

7 INTERIM ANALYSES

A DSMB will be established for the study including physicians knowledgeable in the treatment of PPHN and a statistician. Throughout the course of the study the DSMB will meet on a regular basis to monitor the safety of the study. Meetings will occur as outlined in the DSMB Charter. All analyses will be prepared by an independent external consultant and reviewed only by the DSMB as defined in the DSMB Charter. The Sponsor will only have access to blinded study data during this process. The details regarding the interim efficacy and safety analysis are included in a separate SAP.

8 GENERAL CONSIDERATIONS FOR DATA ANALYSES

All the data collected in the electronic Case Report Form (eCRF) will be listed. In general, listings will be sorted by treatment group, subject number, and scheduled assessment (if applicable). Listings will include assessment date, assessment time (if available), study day, and all relevant data collected in the eCRFs. For data collected on a fixed schedule, the assessment identifier or the nominal time point will also be included on the listing. Repeat or redundant observations within an assessment window and observations that do not fall within any predefined assessment window (and will, therefore, be excluded from summaries) will be flagged in these listings. Subjects who are not to be included in the analysis population (eg, Safety population, Per Protocol population) will be flagged.

In general, the data will be summarized by scheduled assessment (if applicable) within each treatment group. For continuous variables, summary statistics will include the mean, standard deviation, median, minimum, and maximum. For summaries of non-normal data, interquartile range (lower quartile, upper quartile) may also be included. Minimums and maximums will be expressed using the level of precision in which the variable was collected. All other statistics will be rounded, using an additional decimal place than was collected. For discrete variables, summaries will include the frequency and percentage in each category. Percentages will be rounded to 1 decimal place. For all inferential analyses and descriptive comparisons, p-values will be rounded to 4 decimal places. Values less than 0.0001 will be denoted as <0.0001, and values greater than 0.9999 will be denoted as >0.9999 whenever practical. Categories of discrete variables will be ordered and labelled as they appear in the eCRF, and all categories represented on the eCRF will be included in summaries, even when they do not apply to any subjects in the study.

Unless otherwise specified, all statistical tests will be 2-sided at alpha level 0.05. All statistical calculations will be completed using the SAS® Version 9.4 or above.

8.1 COVARIATES

There are no planned covariates.

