3.5 NUMBER OF SUBJECTS

Approximately 70 subjects will be randomized (1:1) to either receive treatment with Remodulin or placebo to provide 66 evaluable neonates. Enrollment will be closed once 66 evaluable subjects have been enrolled. No more than 32 subjects with a diagnosis of PPHN associated with CDH will be enrolled; these subjects will be evenly enrolled (1:1) into the Remodulin and placebo groups.

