5.2 RANDOMIZATION

An Interactive Web Response System (IWRS) will be utilized for the central randomization procedure. Subjects will be randomized in a ratio between active and placebo of 1:1. No more than 32 evaluable subjects with a diagnosis of PPHN associated with CDH will be enrolled; these subjects will be balanced between the treatment groups.

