8.2 EXAMINATION OF SUBGROUPS

If the data permit, analyses may be stratified by presence/absence of congenital diaphragmatic hernia (CDH).

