10.1.1.2 Primary Efficacy Analysis

The frequency and percentage of subjects who experience clinical worsening through Day 14 will be calculated for each treatment group. A chi-square test will be conducted to compare the incidence of clinical worsening between the treprostinil and placebo treatment groups.

The SAS Procedure FREQ will be used. The pseudo SAS statements are listed below:

```
proc freq;
  tables Treatment* Worsening / chisq;
run;
```

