10.1.1.3 Sensitivity and Subgroup Analyses

To further support the robustness and assess the sensitivity of the primary efficacy analysis of clinical worsening through Day 14 (provided that the primary analysis yields significant results),

the above summary and chi-square test will be repeated using each of the following modifications (if data permit):

- The Per Protocol population will be used instead of the ITT population
- PPHN diagnosis (associated with unilateral CDH versus not associated with unilateral CDH)

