10.2.5 Time to Clinical Worsening

Data on the clinical worsening assessment page of the eCRF will be used to determine clinical worsening status. Clinical worsening events including the date (study day) of the event and details of the clinical worsening event will be listed. The time to clinical worsening will be calculated according to the rules specified in [Table 8-1](#).

Time to clinical worsening will be summarized by treatment group using product-limit estimates calculated by the Kaplan-Meier method, and displayed graphically as Kaplan-Meier curves. A tabular summary of this analysis will include the number of subjects at risk (sample size), estimated median duration, and a 95% confidence interval for the median duration for each treatment group. The log-rank test will be used to calculate the p-value for treatment differences.

The SAS Procedure LIFETEST will be used. The pseudo SAS statements are listed below:

```
proc lifetest;
  time TimeToWorsening*Censor_Status(1);
  strata Treatment;
run;
```

In addition, the Cox proportional hazards model will be fit to obtain the hazard ratio. The model will include treatment as an explanatory variable. The SAS procedure PHREG will be used.

The pseudo SAS statements are listed below:

```
proc phreg;
  Model TimeToWorsening*Censor_Status(1) = treatment
    / risklimits alpha=0.05 ties=efron;
run;
```

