10.2.6 Time to Initiation of ECMO

Time to initiation of ECMO will be analyzed as described in Section 10.2.5.

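### CDH is capped and balanced by design, but the SAP commits to no outcome analysis by CDH unless the primary test is significant

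*SAP*

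**What the plan says.** **Design.** Protocol 5.2 limits CDH to 32 evaluable subjects and says "these subjects will be balanced between the treatment groups". Protocol 3.5 says "these subjects will be evenly enrolled (1:1) into the Remodulin and placebo groups". Neither section calls the randomization stratified.

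**Primary analysis.** SAP 8.1: "There are no planned covariates". SAP 10.1.1.2: "A chi-square test will be conducted to compare the incidence of clinical worsening between the treprostinil and placebo treatment groups". The code there is a plain two-by-two table.

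**Time-to-event analyses.** For the Cox model in SAP 10.2.5, "The model will include treatment as an explanatory variable", and the log-rank test has treatment as its only factor. SAP 10.2.6 follows suit: "Time to initiation of ECMO will be analyzed as described in Section 10.2.5". SAP 10.2.7 does the same for iNO.

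**CDH analyses.** SAP 8.2: "If the data permit, analyses may be stratified by presence/absence of congenital diaphragmatic hernia (CDH"). SAP 10.1.1.3 names a CDH versus non-CDH repeat of the primary chi-square, but only "provided that the primary analysis yields significant results", and then only if the data allow it.

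**Outputs.** SAP 15.1 lists clinical worsening for the ITT and Per Protocol populations (Tables 14.2.1.1 and 14.2.1.2). No listed table or figure is broken down by CDH. SAP 9.3.2 summarises PPHN diagnosis at baseline by arm.

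**Change endpoints.** SAP 8.5.2 and 10.2.1 to 10.2.4 compare changes from baseline by t-test, or by Wilcoxon if normality fails, with no baseline term.

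**The concern.** A factor important enough to cap and balance on would normally appear in the analysis. The protocol gives reasons to look at it. Section 1.1 describes CDH as a distinct type of PPHN with hypoplastic vasculature and notes that the two iNO trials it cites enrolled no CDH infants. Section 2.1 frames the primary objective as exploration.

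Up to 32/66 = 48% of evaluable infants may have CDH. If the primary misses, nothing obliges the sponsor to show whether the two groups behaved alike. A breakdown produced then would carry a post-hoc label that a small SAP change now would avoid.

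Two lesser matters go with this. An analysis that ignores a strongly prognostic balanced factor is conservative, and a change score that ignores its baseline may be less precise than it could be.

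**Working it through.** **1. The plan's own figure.** Inputs from Protocol 10.2 and SAP 5: 60% vs 30%, one-sided 0.05, 80% power. With the pooled rate 0.45,

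n per arm = [1.645·√(2·0.45·0.55) + 0.842·√(0.6·0.4 + 0.3·0.7)]² / 0.30² = 32.9, so 33.

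The stated 66 is reproduced, with power 80.1% by the same formula. The SAP test is two-sided (SAP 8 and 10.1.1.1). At two-sided 0.05 the power at 33 per arm is 69.6% by formula and 73.6% by exact binomial enumeration.

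**2. How often the CDH analysis is not triggered.** Probability = 1 − exact power of the uncorrected two-sided chi-square at 33 per arm, placebo 60%:

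| Remodulin rate | Power | Not triggered |
|---|---|---|
| 30% | 73.6% | 26.4% |
| 40% | 41.4% | 58.6% |
| 60% (no effect) | 5.9% | 94.1% |

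**3. Does this depend on the effect differing by CDH?** Assume 60% vs 30% in non-CDH infants and 60% vs 60% in CDH infants, and compare with a uniform effect of the same average:

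| CDH + non-CDH per arm | Average Remodulin rate | Not triggered, effect confined | Not triggered, effect uniform |
|---|---|---|---|
| 16 + 17 | (16·0.6 + 17·0.3)/33 = 44.5% | 72.8% | 72.3% |
| 11 + 22 | (11·0.6 + 22·0.3)/33 = 40.0% | 58.8% | 58.6% |
| 6 + 27 | (6·0.6 + 27·0.3)/33 = 35.5% | 43.5% | 43.5% |

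Now hold the average at 60% vs 30% at 16 + 17, but set Remodulin at 45% in CDH and 15.9% in non-CDH. The probability is 26.0%, against 26.4% when uniform. It follows the average effect.

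**4. Precision of the breakdown** at the cap (16 CDH and 17 non-CDH per arm), 60% vs 30%. The 95% half-width is 1.96·√[(0.6·0.4 + 0.3·0.7)/n]:
- CDH, n = 16: 0.329
- non-CDH, n = 17: 0.319
- difference between strata: √(0.329² + 0.319²) = 0.458

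Exact two-sided power within CDH is 41%.

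**5. Chi-square against a Cochran-Mantel-Haenszel (CMH) test stratified by CDH**, exact, two-sided 0.05, 16 + 17 per arm. The documents give no event rate by CDH, so the placebo gap g (CDH minus non-CDH) is assumed. Placebo rates are 0.60 + g·17/33 in CDH and 0.60 − g·16/33 in non-CDH. Remodulin rates share one odds ratio and average 30%.

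| Gap | Placebo CDH / non-CDH | Power, chi-square | Power, CMH | Size, chi-square | Size, CMH |
|---|---|---|---|---|---|
| 0 | 60% / 60% | 73.6% | 70.3% | 5.9% | 5.4% |
| 30 | 75% / 45% | 74.5% | 74.7% | 4.7% | 5.0% |
| 40 | 81% / 41% | 75.3% | 77.1% | 3.8% | 4.9% |
| 50 | 86% / 36% | 76.4% | 81.4% | 2.8% | 4.9% |

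**6. Baseline adjustment.** With complete data, the variance ratio of ANCOVA to change score is (1 − ρ²)/(1 + k² − 2ρk), where ρ is the baseline to follow-up correlation and k is baseline SD over follow-up SD. Neither is given. At assumed ρ of 0.3 / 0.5 / 0.8 the ratio is 0.65 / 0.75 / 0.90 for k = 1, and 0.96 / 1.00 / 0.80 for k = 0.5.

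**The case against.** The strongest reply is that nothing is prohibited. SAP 8.2 allows any analysis to be stratified by CDH whatever the primary shows, the SAP preface allows additional analyses, and PPHN diagnosis and worsening events are both listed by subject. Sections 8.2 and 10.1.1.3 are compatible, one a general permission and the other a specific conditional analysis. All of this stands, and it narrows the point to the absence of a commitment.

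A reader might go further and infer that the condition is most likely to fail exactly when the effect differs by CDH. Step 3 refutes this: failure follows the average effect and is commonest when there is no effect at all.

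A reader might also infer that leaving CDH out of the primary test biases or invalidates it. It does not. The chi-square's size is at most 5.9% in the scenarios of step 5, and it becomes conservative as CDH becomes more prognostic, so a positive result stands. At a gap of zero CMH has 3.3 points less power (73.6% − 70.3%), with slightly lower size, and it shows no material gain up to a gap of 30 points. This argues against making CMH the primary test.

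Finally, the breakdown would be imprecise, and the secondary tests run only after a significant primary (SAP 8.4). Both are true. The first is why the table should be descriptive. The second is why stratified secondary tests and ANCOVA do nothing for the missed-primary case.

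**Conclusion.** The point holds as a gap in commitment and reporting, worth considering before unblinding. On the text alone, no outcome analysis by CDH is assured after a non-significant primary, and even after a significant one it depends on the data allowing it.

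The probabilities of 26.4%, 58.6% and 94.1% assume one look at 33 per arm, complete outcomes and the SAP's two-sided test. They ignore the efficacy and futility look in SAP 4, whose rules are in a separate DSMB plan, and the rule in SAP 8.3.1 that counts missing outcomes as worsening. If the trial stops at 40 subjects, SAP 4 applies this same plan, condition included.

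The gain from stratifying is material only under an assumed placebo gap of 40 to 50 points (about 2 to 5 points of power), for which the documents offer no evidence. The baseline-adjustment point is minor: its gain depends on an unknown correlation and SD ratio and may be near zero.

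**What to change.** Before unblinding:

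1. In SAP 10.1.1.3, remove the significance condition for the CDH analysis and align 8.2 with it. Add to 15.1 a table of clinical worsening by CDH and arm, with risk differences and confidence intervals, labelled descriptive and reported whatever the primary result.
2. Keep the chi-square as primary and keep the planned log-rank and Cox analyses. Add as supporting a CMH test (`tables CDH*Treatment*Worsening / cmh`), a CDH-stratified risk difference with its interval, and CDH-stratified log-rank and Cox analyses beside those in 10.2.5 to 10.2.7.
3. Minor: in 10.2.1 to 10.2.4 use ANCOVA with the baseline value (log scale for NT-proBNP). Name the fallback for non-normal data, either a rank-based ANCOVA or the existing Wilcoxon test. State that this does not address OI missing after extubation or loss of arterial access, or the LOCF imputation.
4. Amend 8.1 to match.

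The cost is SAP wording, one table and a few lines of SAS, with no new data and no change to the primary test. The main risk is over-reading a breakdown with half-widths of about 33 points in CDH and 46 for the difference between strata, which the descriptive label and the intervals should limit.

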8.2 EXAMINATION OF SUBGROUPS

If the data permit, analyses may be stratified by presence/absence of congenital diaphragmatic hernia (CDH).

8.3 PREMATURE DISCONTINUATION AND MISSING DATA

8.3.1 Missing Data Handling for Primary Efficacy Endpoint

Any subject with a missing value for clinical worsening will be assigned a value of “Yes.”

8.3.2 Missing Data Handling for Secondary Efficacy Endpoints

For any continuous secondary endpoint, missing values will be imputed using last observation carried forward (LOCF). If an assessment is missing at Baseline, change from Baseline will not be calculated and the subject will not be included in the analyses of this assessment.

Time to event will be derived as detailed in Section 8.5.3.

8.4 MULTIPLE COMPARISONS AND MULTIPLICITY

The primary efficacy endpoint of clinical worsening through Day 14 will be tested at alpha level 0.05. If the primary efficacy endpoint is statistically significant at alpha level 0.05, the statistical tests for secondary efficacy endpoints will be performed. As these comparisons are exploratory, no adjustments for multiplicity are planned.

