10.2 SAMPLE SIZE

Based on the systematic review of use of nitric oxide for respiratory failure in infants by Finer and Barrington, 57.9% (194/335) subjects in control group had an outcome of death or requirement for EMCO (18). In this study, assuming 60% subjects in placebo group and 30% subjects in Remodulin group with an outcome of death, requirement for EMCO, or need for additional PAH therapy, we calculated that 66 subjects (33 subjects per treatment group) will have at least 80%

power to show a significant difference in favor of Remodulin at alpha level of 0.05 (one-sided test). Approximately 70 subjects are planned to be randomized (1:1) to either receive treatment with Remodulin or placebo on top of the standard of care.

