10.4 INTERIM ANALYSIS

A safety review will be conducted by a Data Safety Monitoring Board (DSMB) after the first 10 subjects have been randomized to receive study drug and have completed the 14-day study period. A second review will occur once 40 subjects have been enrolled and completed the 14-day study period. Ad hoc meetings may be scheduled at additional enrollment milestones or in response to events related to the safety of study treatment.

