4 SEQUENCE OF PLANNED ANALYSES

Interim Safety Analyses

A safety review will be conducted by a Data Safety Monitoring Board (DSMB) after the first 10 subjects have been randomized to receive study drug and have completed the 14-day treatment period. A second review will occur once 40 subjects have been enrolled and completed the 14-day treatment period. Ad hoc meetings may be scheduled at additional enrollment milestones or in response to events related to the safety of study treatment.

Interim Efficacy and Futility Analyses

Efficacy and futility will be assessed at the second formal data review. Details of the planned analyses and stopping rules are specified in the DSMB SAP. If the DSMB votes to stop the study at the second review, all analyses will be conducted as specified in this SAP on the 40 available subjects. Otherwise, these analyses will not be conducted until the study is completely enrolled.

Final Analysis after Database Lock and Study Unblinding

After the database has been quality assured and locked, the treatment assignments will be provided to the Sponsor's project statistician by the central randomization service and all planned analyses described in this document will be performed. By intent, no changes will be made to the clinical database after unblinding. However, any changes that are deemed necessary, after unblinding, will be clearly documented in the CSR.

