5 SAMPLE SIZE CONSIDERATIONS

Based on the systematic review of use of nitric oxide for respiratory failure in infants by Finer and Barrington (2006), 57.9% (194/335) subjects in the control group had an outcome of death or requirement for ECMO (Finer 2006). In this study, assuming 60% of subjects in the placebo group and 30% of subjects in the Remodulin group with an outcome of death, requirement for ECMO, or need for additional PH therapy, we calculated that 66 subjects (33 subjects per treatment group) will have at least 80% power to show a significant difference in favor of Remodulin at alpha level 0.05 (1-sided test). Approximately 70 subjects are planned to be

randomized (1:1) to either receive treatment with Remodulin or placebo in addition to the standard of care.

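### The SAP adds an efficacy look at 40 subjects but keeps an unadjusted two-sided 0.05 for the primary test, so it does not show that the 5% level is protected

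*SAP*

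**What the plan says.** Protocol 10.4 is headed as an interim analysis, but its content is DSMB safety review, first after 10 subjects and then later: "A second review will occur once 40 subjects have been enrolled and completed the 14-day study period". Protocol 10.7 likewise gives the DSMB a safety remit. Neither mentions an efficacy or futility test.

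SAP section 4 adds one at the 40-subject review: "Efficacy and futility will be assessed at the second formal data review". It places the stopping rules in a DSMB SAP and says that, if the DSMB stops the study there, the analyses of the main SAP are run on the 40 subjects. SAP section 7 confirms the split: "The details regarding the interim efficacy and safety analysis are included in a separate SAP".

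On the level, SAP 8.4 states: "The primary efficacy endpoint of clinical worsening through Day 14 will be tested at alpha level 0.05". SAP section 8 adds: "Unless otherwise specified, all statistical tests will be 2-sided at alpha level 0.05". SAP 10.1.1 gives a two-sided hypothesis and a plain chi-square test. Neither document gives an interim level, a spending function, a reduced final level, or a statement that the look cannot stop for efficacy. The sample-size text (Protocol 10.2, SAP 5) uses 0.05 one-sided and mentions no interim look.

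**The concern.** An efficacy look that can stop the trial gives the primary endpoint two chances to be declared significant. If the final test still uses the whole 0.05, the probability of at least one false rejection exceeds 0.05 unless something else, such as a binding futility rule, takes it back. On an early stop, a literal reading of SAP 4 with 8.4 would also compare the 40-subject p-value with 0.05 rather than with the bound that justified stopping.

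More than one p-value depends on this. SAP 8.4 makes testing of the secondary endpoints conditional on a significant primary result, and SAP 10.1.1.3 does the same for the sensitivity and subgroup analyses. An error in the primary claim therefore carries through the rest of the efficacy reporting.

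**Working it through.** **1. The plan's own figure.** Inputs from Protocol 10.2: "assuming 60% subjects in placebo group and 30% subjects in Remodulin group", one-sided 0.05, 80% power. The pooled rate is 0.45.

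n per arm = [1.645·√(2·0.45·0.55) + 0.842·√(0.6·0.4 + 0.3·0.7)]² / 0.30² = (1.157 + 0.565)² / 0.09 = 32.9, so 33 per arm and 66 in total, with power 80.06%. The figure is reproduced, and it is a single-look calculation with no allowance for an interim test.

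**2. Information at the look.** 40/66 = 0.606 and 40/70 = 0.571. The correlation between the interim and final statistics is the square root: 0.778 and 0.756.

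**3. Type I error with the final test left at 0.05.** Overall error = 1 − P(|Z1| < c1 and |Z2| < 1.96), with (Z1, Z2) bivariate normal. The interim bound c1 is an assumption, because the documents do not give it. No binding futility stop is assumed.

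| Assumed interim two-sided level | Overall error, 40/66 | Overall error, 40/70 |
|---|---|---|
| 0.05 | 7.94% | 8.06% |
| O'Brien-Fleming-type (0.0118; 0.0095 at 40/70) | 5.42% | 5.35% |
| 0.005 | 5.12% | 5.14% |
| 0.001 | 5.01% | 5.01% |

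The O'Brien-Fleming-type level is 2[1 − Φ(1.96/√0.606)] = 2[1 − Φ(2.518)] = 0.0118.

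**4. Final level that restores 0.05.** Solve the same expression for the final bound. At 40/66:

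- interim 0.0118 needs final 0.0455;
- interim 0.005 needs 0.0487;
- interim 0.001 needs 0.0499.

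The other common convention spends 0.025 on each side and gives interim 0.0080 and final 0.0475.

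**5. Effect of a binding futility rule.** As an illustration only, suppose the trial must stop whenever the interim estimate favours placebo, with an interim rejection against Remodulin still counted. With final 0.05 at 40/66, the overall two-sided error is 6.5% (interim 0.05), 3.3% (O'Brien-Fleming-type) and 2.6% (interim 0.001). The direction of the net effect therefore depends on the unseen rule.

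**6. Direction.** Counting only false rejections in favour of Remodulin, two looks at two-sided 0.05 spend 3.97% (40/66) or 4.03% (40/70). That is below the one-sided 5% used for sample size. One-sided 0.05 at both looks would give 7.6% or 7.8%.

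**7. Small-sample check.** Exact enumeration with 20 and then 33 per arm, uncorrected chi-square and 0.05 at both looks gives 8.4% to 8.6% for common event rates of 30%, 45% and 60%. A single look gives 5.3% to 6.3%.

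**The case against.** The strongest reply is that the deciding rule is in a document not seen here, rather than missing. The DSMB SAP may hold a strict boundary, an adjusted final level or a binding futility rule. This stands as a limit on size and direction. It does not settle the wording of the main SAP: a reduced final level in the DSMB plan would conflict with SAP 8.4, and if there is none, SAP 8.4 needs to say why 0.05 can be kept.

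A reader might infer that the false-positive rate is certainly inflated, or that it is about 8%. The documents support neither. The 8% figure needs an interim test at the full 0.05, which is stated nowhere. At p<0.001 the excess is 0.01 points, less than the discreteness error of the uncorrected chi-square itself (step 7).

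A reader might also infer that a p-value under 0.05 at 40 subjects triggers an efficacy stop. SAP 4 says only that the SAP's analyses are then run on those subjects; what triggers stopping is left to the DSMB SAP. Nor is the remark in SAP 8.4 that no multiplicity adjustment is planned a decision about the look, since it follows the sentence on secondary comparisons.

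The sidedness argument is fair: in Remodulin's favour the worst case shown stays within one-sided 5%. But the analysis sections specify a two-sided test, so the plan has to choose. The exploratory Phase II aim lowers the stakes without removing them, because SAP 8.4 defines significance and makes other tests depend on it.

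**Conclusion.** The point holds as a conditional one. The plan adds an efficacy look, leaves the primary test at an unadjusted two-sided 0.05, and shows nothing that protects that level. With no binding futility rule, the two-sided error runs from 5.01% to about 8% over the interim bounds considered; under conventional strict bounds the excess is at most about 0.4 points. A binding futility rule could take it below 5%. These figures assume looks at 40 and at 66 or 70 subjects and the normal approximation. The level at risk is the SAP's two-sided 0.05, not the one-sided 0.05 of the sample-size section. That Protocol 10.4 and SAP 4 describe the 40-subject review differently is certain and does not depend on the boundary.

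**What to change.** - **SAP 8.4 and 10.1.1.2:** state the final critical value net of the efficacy boundary in the DSMB SAP, and cross-refer to that plan so the two agree. Examples at 40/66 are interim p<0.0118 with final p<0.0455 (Lan-DeMets O'Brien-Fleming spending), or interim p<0.001 with the final level kept at about 0.05 (0.0499 exactly). Alternatively, state that the look cannot stop for efficacy.
- **Same sections:** say whether the protected level is two-sided or one-sided 0.05, and whether the futility rule is binding. Do not count on a non-binding rule to recover alpha.
- **SAP 4:** state that an early efficacy stop is judged against the interim bound, not 0.05.
- **Protocol 10.4:** describe the efficacy and futility look.

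The cost is wording, to be settled before unblinded efficacy data are reviewed. The power loss is small. With 33 per arm, power = Φ{[0.30 − z·√(2·0.45·0.55/33)] / √(0.45/33)}, which is 69.6% at two-sided 0.05 (z = 1.96) and 68.1% at 0.0455 (z = 2.00). That is a loss of about 1.5 points at the final test, before crediting the chance of rejecting at the interim. With an interim bound of p<0.001 the loss is negligible.
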